# **SYNOPSIS**

Sponsor	Island Pharmaceuticals, Ltd
Study Title	A Phase 1a, randomized, double-blind placebo-controlled study to evaluate safety and tolerability and to characterize the pharmacokinetic profile of single ascending doses of fenretinide oral capsules in healthy adult volunteers.
Protocol Number	ISLA101-P01-CT001
IND Number	142758
Indication	Prophylaxis of dengue fever
Sites	One study center located in Australia. A contract research organization will oversee operational aspects of this study on behalf of Island Pharmaceuticals, the sponsor of the study.
Phase of Development	Phase 1a
Study Type	Interventional
Objectives	
 
The primary objective is to:
 
Evaluate the safety and tolerability of single ascending doses (SAD) of ISLA101 in healthy adult volunteers (fasted).
 
The secondary objective is to:
 
Characterize the pharmacokinetic (PK) profile (fasted) of fenretinide after administration of SAD of ISLA101 in healthy adult volunteers (fasted).
 
The exploratory objective is to:
 
Assess the PK profile of fenretinide in healthy adult volunteers under fed conditions.
 

Endpoints	
 
The primary endpoints are:         
 
Vital signs, clinical laboratory tests, changes from baseline in physical examinations, adverse events (AEs), and treatment emergent adverse events (TEAEs).
 
 
 
The secondary endpoints are:         
 
Single dose PK parameters for fenretinide in plasma: Cmax, Tmax, AUClast, AUCinf, T1/2, and others as relevant.
 
 
 
The exploratory endpoints are:         
 
Single dose PK parameters for fenretinide in plasma under fed conditions: Cmax, Tmax, AUClast, AUCinf, T1/2, and others as relevant.
 
 
 

Study Design and Treatment	This study is a randomized, double-blind, placebo-controlled SAD study. There are 3 planned dose-level cohorts (Cohorts 1-3). Each dose-level cohort will consist of 8 subjects (6 active + 2 placebo), who will be treated under fasted conditions. The subjects in the highest tolerated dose-level cohort will also be administered ISLA101 under fed conditions, in a cross-over manner (Cohort 4). Proposed doses are 300, 600, and 900 mg/m² (equivalent to 8.1, 16.2, and 24.3 mg/kg). Each subject will be allocated to 1 dose level only.  The study will include a 5-day stay in the clinical research unit followed by a final safety follow-up visit at Day 8.  An independent Safety Review Committee (SRC) will review available safety data up to 96-hours post-dose for subjects enrolled in each dose-level cohort. After safety review, the dose level may be escalated to the next planned or lower than

planned dose level, de-escalated to an intermediate dose level, or repeated at the same dose, if needed.

The first 3 dose-level cohorts will be treated under fasting conditions. A single dose of study drug will be administered on the morning of Day 1, after an overnight fast of approximately 10 hours, followed by an additional 4-hour fast after dosing. Study drug will be taken with up to 8 oz/240 ml of water. Water will be allowed ad libitum except the interval from 1 hour before to 1 hour after dosing.

Following review of the safety data of the highest tolerated dose level, the subjects enrolled in this dose-level cohort will be recalled to evaluate the PK of ISLA101 dosed under fed conditions (Cohort 4; 8 subjects). These data will support a planned Phase 2 study. Subjects will be informed and will be provided a consent form prior to the participation in the food effect cohort (Cohort 4) of the study.

Subjects in Cohort 4 will be dosed after a meal. They will fast overnight for at least 10 hours and will then consume a high-fat, high-calorie meal prior to administration of study drug, as outlined in the FDA's Guidance for Industry- Assessing the Effects of Food and Drugs in INDs and NDAs – Clinical Pharmacology Considerations. The study drug should be administered approximately 30 minutes after start of the high-fat meal. No food consumption will be permitted for at least 4 hours post-dose. Water will be allowed ad libitum except the interval from 1 hour before to 1 hour after dose.

# **Study Population**

Approximately 24 healthy male and female volunteers who are 18–65 years of age (inclusive).

#### **Inclusion Criteria**

Subjects must meet the following criteria to be enrolled in the study:

- 1. Healthy male or female volunteers not of childbearing potential, who are 18 years to 65 years of age (inclusive) at the time of signing the informed consent form (ICF).
- 2. Females not of childbearing potential, as defined in the following criteria:
  - a. History of hysterectomy.
  - b. Post-menopausal.
    - i. Natural post-menopausal females with at least 12 months from natural spontaneous amenorrhea and a serum follicle-stimulating hormone (FSH) concentration ≥ 40 IU/L.
    - ii. Post-surgical females must have undergone bilateral oophorectomy at least 6 weeks prior to study.
- 3. Male subjects with female partners of childbearing potential must agree to practice abstinence or use a combination of 2 of the following acceptable birth control methods during the study and for at least 90 days after dosing:
  - a. Partners have an intrauterine device (IUD) without hormones in place for at least 3 months.
  - b. Barrier method (condom or diaphragm) for at least 14 days prior to screening and 90 days after dosing with study drug.
  - c. Partners using stable hormonal contraceptive for at least 3 months prior to screening and for 90 days after dosing with study drug.
  - d. History of vasectomy at least 3 months prior to signing the ICF.
- 4. Must be able to understand and provide signed informed consent for study participation.
- 5. Willing and able to comply with all scheduled visits, treatment plan, laboratory tests, and other study procedures.

- 6. Body mass index (BMI) 18.0 to 32.0 kg/m^2 (inclusive), and a body weight  $\geq$  50 kg.
- 7. Normal renal function, defined as estimated glomerular filtration rate (eGFR)  $\geq$  70 mL/min/1.73 m^2 at screening and Day -1.
- 8. Clinical laboratory values should be within the laboratory's stated normal range. If not within this range, they must be without clinical significance, as determined by the Investigator.
- 9. No history of clinically relevant medical disorders, as determined by the Investigator.

#### **Exclusion Criteria**

A subject will be excluded from the study if he or she meets any of the following criteria:

- 1. Known or suspected pregnancy (confirmed via a positive serum human chorionic gonadotropin [hCG] pregnancy test at screening), planned pregnancy during the study period, nursing, or lactation.
- 2. Women of childbearing potential or men who intend to father a child or donate sperm during the study period and for 3 months after study drug administration.
- 3. Known allergy to fenretinide or any of the components of ISLA101.
- 4. Evidence or history of clinically significant medical conditions, such as hematological, renal, endocrine (e.g., polycystic ovarian syndrome or other anovulatory states), immunologic, pulmonary, metabolic, gastrointestinal (e.g., Crohn's disease, acute or chronic pancreatitis, and others) and surgery (except for simple appendectomy or repair of a hernia), which all can influence the absorption of study drug; cardiovascular, hepatic, psychiatric, neurologic, or allergic disease (including drug allergies, but excluding untreated, asymptomatic, seasonal allergies at the time of dosing), or any other illness that the Investigator considers exclusionary or that could interfere with the interpretation of the study results.
- 5. History of severe infectious disease or recurrent infections.
- 6. Aspartate transaminase (AST), alanine aminotransferase (ALT), or total bilirubin above the 1.5 x upper limit of normal (ULN) at screening and Day -1.
- 7. Clinically significant electrocardiogram (ECG) abnormalities or vital sign abnormalities at screening and Day -1, long QT syndrome, or a history of cardiac disease.
- 8. Abnormal diet that may affect absorption, distribution, metabolism, or excretion of drugs, for example, lacking standard nutrients (e.g, cleansing diet 2 weeks before or during the study).
- 9. Positive result for hepatitis B, hepatitis C, or human immunodeficiency virus (HIV) at screening.
- 10. History of positive test for tuberculosis (TB) at screening.
- 11. A subject who has donated 1 unit of blood of over 500 mL within 56 days prior to the study drug administration, or donated plasma within 14 days prior to study drug administration.
- 12. Use of systemic antibiotics within 30 days prior to dosing.
- 13. Any use of drugs that inhibit or induce CYP enzymes within 30 days prior to administration of study drug and for the duration of study participation.
- 14. Use of any tobacco products, e-cigarettes, and/or nicotine replacement products in the 3 months preceding screening.
- 15. Any food allergy, intolerance, or restriction that, in the opinion of the Investigator, could contraindicate the subject's participation in this study.

	16. Recent history of (within the past 12 months), or strong potential for, alcohol or substance abuse. Alcohol abuse will be defined as > 14 drinks per week (1 drink = 10g of ethanol).							
	17. History of drug or alcohol abuse within 5 years before screening or positive result of UDS (e.g, amphetamines, benzodiazepines, cannabinoids, cocaine, hallucinogens, opiates) or alcohol breath test at screening.							
	18. Exposure to any investigational agent or used an invasive investigational medical device within 30 days or within a period less than 5 drug half-lives prior to study entry (whichever is longer).							
	19. Study site employees, Sponsor's employees, or immediate family members of a study site or Sponsor employee.							
	

20. Previously enrolled in this study.

21. Vaccination within 14 days from screening or plans to get a vaccine within 30 days after dosing.

							
	22. Acute infection (such as influenza) or relevant lesion at the time of Screening or Day -1. Subjects can be rescreened once they have recovered.							
	23. Criteria at the discretion of the Investigator:							
	a. Chronic medical condition that impacts subject safety.							
	

b. Clinically significant abnormal physical examination or vital signs at screening.

c. Condition believed to interfere with the subject's ability to provide

							
	informed consent or comply with study instructions, or that might confound the interpretation of the study results or put the subject at undue risk.							
	d. History or evidence of a clinically significant disorder, condition, or disease that that is believed to significantly impair pain perception (e.g., history of stroke, history of neuropathy), would pose a risk to subject safety or interfere with evaluation, procedures, or study completion.							
Duration of Treatment	The study participation will last for a total duration of approximately 6 weeks, including screening, confinement, and a follow-up period.							
	The screening period may last up to 28 days. The confinement period will be approximately 5 days. The follow-up period is up to 3 days.							
	The follow-up period after highest tolerated dose cohort will serve as the washout period for the food effect cohort.							
	For the food effect cohort, an additional confinement period of approximately 5 days will be required, followed by a follow-up period of up to 3 days.							
Study Drug, Dose,	Dosing will begin with a dose level of 300 mg/m  of fenretinide administered via							
and Mode of Administration	oral capsules. The decision to advance to the next cohorts (600 mg/m² and							
Number of Subjects	900 mg/m  ) will be based on safety and tolerability data reviewed by the SRC.  Approximately 24 subjects will be enrolled in total. Subjects who withdraw or are							
Trumber of Subjects	removed from the study, except for safety reasons, may be replaced at the discretion of the Sponsor.							

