PK sampling to assess the PK of fenretinide will be performed at the time points as specified in Table 2.

Monitoring for serious adverse events begins when the informed consent form is signed; and treatment-emergent adverse events begins after the first dose is administered.

 Study day is relative to study drug administration for the subjects in Cohort 3.

Study Schedule and Sampling Time Points for Pharmacokinetic Analysis Table 2

	-1 0.5 0.75 1 1.5 2 3 4 5 6 8 10 12 24 36 48 72	+/-5 +/-15				X							
	Time Relative to Dose (hours) a $\begin{bmatrix} -1 & 0.5 & 0.75 \end{bmatrix}$	Assessment Window (minutes) b +/-2	1	2	3	4	5	10 X X X	11	12	13	14	
1				£-I	8 1 10		в П 1	ւ Տ ր ոդ		hor	Co		

a: Time from dose begins when first capsule is consumed

b: Vital signs should be assessed prior to PK samples taken

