Subjects will be discharged from the clinic on Day 5. At the discretion of the Investigator or designee, the confinement time can be extended to ensure the safety of each subject. Subjects will have up to 3 days of follow up. For Cohort 4 (the food effect cohort), the confinement and follow-up visit will be repeated. Subjects who are dosed but withdrawn prior to study completion will participate in an Early Termination visit and may be replaced if needed to obtain sufficient information as possible based on the timing.

In all cohorts, safety will be assessed via vital signs, clinical laboratory tests, physical examinations, AEs, and TEAEs. Pharmacokinetic data will be collected and analyzed at the end of the study but will not be used for dose escalation decisions. A description of study assessments is provided in Table 1.

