## 8.1 Study Assessments by Visit

For subjects who participate in Cohort 4 (the food effect cohort), the assessments described on Days -1, 1, 2, 3, 4, 5, and 8 will generally be repeated on Days 9, 10, 11, 12, 13, 14, and 17, respectively, unless noted otherwise in the Schedule of Assessments (Table 1).

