### 4.3 Pharmacokinetic Parameters

The PK parameters described in this section will be derived based on the plasma concentration-time profiles of fenretinide, MPR and oxo-HPR as observed after the study drug administrations on Day 1 for Cohort 1-3 and Day 10 for Cohort 4 if the data permits using actual timepoints for PK samples. The parameters will be calculated separately for each cohort based on concentrations collected during the specific period.

The PK concentrations will be processed using standard noncompartmental analytical procedures to derive the required parameters. The software used for the analysis will be Phoenix™ WinNonlin® v8.4.0 or greater (Certara, Princeton NJ, USA). Extravascular plasma model with linear up log down trapezoidal rule will be utilized.

The PK parameters described in Table 4 will be derived for the analytes (fenretinide, MPR and oxo-HPR) provided that the required concentration data are available. Supporting PK parameters (used to derive or assess the validity of  $\lambda_z$  and associated parameters) which include Adjusted R^2, number of points for estimation of  $\lambda_z$  or Kel, %AUCextrap and span (ratio of time interval to estimate  $\lambda_z$  to t1/2) will only be listed and not included in the summary tables. %AUCextrap < 20% will be used to validate AUCinf and parameters derived from AUCinf.

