**Table 5 Study Treatments – Tables and Figures**

Cohort: Actual Treatment	Treatment Label
Cohort 1: ISLA101 300 mg Fasted	ISLA101 300 mg Fasted
Cohort 2: ISLA101 600 mg Fasted	ISLA101 600 mg Fasted
Cohort 3: ISLA101 900 mg Fasted	ISLA101 900 mg Fasted
Cohort 4: ISLA101 TBD* mg Fed	ISLA101 TBD* mg Fed
Cohort x/4: ISLA101 TBD* mg	ISLA101 TBD* mg Fasted/Fed
Cohort 1-3: Placebo	Pooled Placebo
Cohort 4: Placebo (Fasted)	Placebo (Fasted)
Cohort 4: Placebo (Fed)	Placebo (Fed)
Cohort 1-3	All Subjects

\*One of the Cohort 1 to 3 Subjects (the highest tolerated dose-level cohort) will return for additional dose to determine the effect of food. Subjects participating in Cohort 4, the food effect cohort, will maintain the same treatment assignment from their fasted cohort.

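### The fed check-in window (Day 9 ±3) overlaps the Day 8 ±1 follow-up that is meant to be the washout, and the fed-period days are tied to Cohort 3 whichever cohort is recalled

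*Protocol*

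**What the plan says.** **Washout.** The protocol Synopsis (Duration of Treatment) states: "The follow-up period after highest tolerated dose cohort will serve as the washout period for the food effect cohort". The same entry gives the length: "The follow-up period is up to 3 days". That period runs from discharge (Section 3.1: "Subjects will be discharged from the clinic on Day 5") to the Synopsis's "final safety follow-up visit at Day 8". No washout is given in hours or half-lives. Section 7.2 mentions a washout between administrations but gives it no length.

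**Visit windows.** Table 1 (read here from the SAP's copy in Section 2.5; the protocol's table has the same layout) sets follow-up at Day 8 ±1 and fed check-in at Day 9 ±3. Protocol Section 8.1 says the assessments of Days -1, 1, 2, 3, 4, 5 and 8 "will generally be repeated on Days 9, 10, 11, 12, 13, 14, and 17, respectively", so the fed dose is given the day after fed check-in.

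**Which cohort.** Footnote 9 to Table 1 says: "Study day is relative to study drug administration for the subjects in Cohort 3". Protocol Section 10.6 likewise names Cohort 4 against Cohort 3 as the food-effect comparison. The Synopsis (Study Design) and SAP Section 6.9.2 instead recall whichever cohort had the highest tolerated dose, and the note to SAP Table 5 says: "One of the Cohort 1 to 3 Subjects (the highest tolerated dose-level cohort) will return for additional dose to determine the effect of food".

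**Analysis.** SAP Section 6.9.2 and Appendix 2 fit food as the only fixed effect, with subject as a random effect.

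**The concern.** A washout should lie between the two doses. Here the period named as the washout ends with a visit that the windows allow to fall after the next dose. Two things are at stake.

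- **The food-effect ratio.** All recalled subjects receive the fasted dose first and the fed dose second. Period and carryover are therefore inseparable from food, and the model has no term for either. Residual drug can only add to fed concentrations, so any bias in fed/fasted is upward, and it varies with each subject's interval. The note to Table 14.2.4 in the table shells draws its conclusion from whether the point estimates leave 80–125%, so a shift in the estimate feeds straight into that reading.
- **Fasted safety.** The primary objective is safety and tolerability of the fasted doses. If the fed dose has already been given when the fasted follow-up takes place, findings at that visit cannot be assigned to the fasted period.

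The Cohort 3 anchor is a separate fault. If another cohort is recalled, the fed-period days are counted from a dose its subjects did not receive.

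**Working it through.** **1. The plan's own figure.** Day 8 − Day 5 = 3 days, which reproduces the stated follow-up length. With the ±1 window it is 2 to 4 days.

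**2. Order of visits.** Follow-up may fall on Days 7, 8 or 9; fed check-in on Days 6 to 12. That gives 7 × 3 = 21 combinations, written (check-in, follow-up).

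- Check-in before follow-up: (6,7), (6,8), (6,9), (7,8), (7,9), (8,9), which is 6 of 21.
- The fed dose day is check-in + 1. In (6,8), (6,9) and (7,9) it is before the follow-up day; in (6,7), (7,8) and (8,9) it is the follow-up day itself.
- In 3 more, (7,7), (8,8) and (9,9), check-in and follow-up coincide.

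This counts what the windows permit. It is not a probability.

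**3. Dose-to-dose interval.** The fasted dose is on Day 1 and the fed dose on check-in day + 1, so the interval is check-in day × 24 h.

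- Earliest: 6 × 24 = 144 h
- Nominal: 9 × 24 = 216 h
- Latest: 12 × 24 = 288 h

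**4. Residual drug.** The documents give no half-life for fenretinide, MPR or oxo-HPR, so half-life is an assumption. With mono-exponential decline, the residual fraction is 2^(−interval / half-life).

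| Assumed half-life | 144 h | 216 h | 288 h |
|---|---|---|---|
| 12 h | 0.02% | <0.01% | <0.01% |
| 24 h | 1.6% | 0.2% | 0.02% |
| 36 h | 6.3% | 1.6% | 0.4% |
| 48 h | 12.5% | 4.4% | 1.6% |

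Under this model each carried-over concentration is that fraction of the corresponding fasted one. The fed/fasted AUC ratio for a subject dosed at that interval therefore rises by about that many percentage points. With no true food effect, 100% at 144 h would read about 101.6%, 106.3% or 112.5% for 24, 36 or 48 h.

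The only half-life yardstick in the documents is five half-lives, in the exclusion criterion on prior investigational agents. Applied here purely for scale, it is met if the half-life is at most 144/5 = 28.8 h, 216/5 = 43.2 h or 288/5 = 57.6 h.

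**5. Recall of a lower cohort.** Suppose Cohort 3 is dosed, found not tolerated, and Cohort 2 is recalled. Protocol Section 3.3 requires 96 h data on at least 7 subjects before progression. Cohort 2 reaches 96 h on its Day 5. With r days for each safety review, Cohort 3 is dosed on Cohort 2's Day 5 + r at the earliest. Its 96 h data come 4 days later, and the recall decision falls on Cohort 2's Day 9 + 2r.

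- r = 0: Day 9
- r = 1: Day 11
- r = 2: Day 13, outside Days 6–12

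So if Day 9 ±3 is counted from Cohort 2's own dose, there is almost no time for review. The shortest interval is then (9 + 2r) × 24 = 216, 264 or 312 h. If days are counted from the Cohort 3 dose, as footnote 9 says, the earliest check-in is Cohort 2's Day 10, giving 240 h. Either way the interval is longer than 144 h.

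**The case against.** The strongest reply is that the intended order is clear. Follow-up is named as the washout, and Section 8.1 lists the fed days as repeats after Day 8. Recall needs a safety review, fresh consent and an eligibility check, so a Day 6 check-in would be an extreme case. A fed pre-dose PK sample is scheduled (SAP Table 3) and summarised, so residual drug would be seen, and SAP Section 3.2 allows case-by-case assessment of issues that may affect PK. Food effect is only an exploratory objective.

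Much of this stands and limits the weight of the point, but it does not remove the contradiction. The windows permit what the washout statement excludes, and nothing fixes the order. Neither SAP Section 4.2 nor 6.9.1 says what to do with a measurable pre-dose value. PK is analysed only after all cohorts finish (Synopsis, Pharmacokinetic Evaluation), so the study's own data cannot support the interval before fed dosing.

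Four stronger readings are tempting, and the documents do not support them.

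- **Drug will still be present at the fed dose.** This needs a half-life, and none is given. At 24 h or less the residual is under 2% even at 144 h.
- **The SAP implies half-lives up to about 41 h.** SAP Section 4.3 says an extrapolated share below 20% "will be used to validate AUC inf and parameters derived from AUC inf". Solving 2^(−96/half-life) = 0.2 gives 96 × ln 2 / ln 5 = 41.3 h. But this is a reporting filter applied to each profile, not an expected half-life. It also sits beside a rule that Span be at least 2: if the terminal phase starts at 24 h, that caps the half-life at (96 − 24)/2 = 36 h.
- **Recalling a lower cohort worsens carryover.** Step 5 shows that it lengthens the interval.
- **The fasted follow-up may be skipped.** Table 1 schedules it and no passage allows its omission. If it coincided with fed check-in, the check-in assessments cover every follow-up item.

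**Conclusion.** The contradiction stands on the text alone and needs no assumption: the follow-up visit that closes the stated washout can fall on or after the day of the fed dose, in 6 of 21 permitted combinations. The Cohort 3 anchor also conflicts with the recall rule. That is a separate scheduling and labelling fault, with no effect on carryover.

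The direction of any bias in fed/fasted is upward. Its size is conditional on an assumed half-life and mono-exponential decline: about 2 percentage points or less at 144 h for half-lives up to 24 h, about 6 at 36 h and 12.5 at 48 h. At the nominal 216 h the corresponding figures are about 0.2, 1.6 and 4.4. These points are fractions of fasted exposure, so if food raises exposure the relative bias is smaller; a doubling halves it. The matter is worth settling because the Synopsis says the fed data support a planned Phase 2 study, and because attribution of fasted follow-up findings touches the primary objective.

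**What to change.** Reconcile these places so that they describe one schedule: the Synopsis washout statement, the Day 8 and Day 9 windows in Table 1 (protocol and SAP copies), footnote 9, Section 8.1 and the comparison in Section 10.6. After the change, the follow-up and fed check-in windows should agree with the stated washout, and the fed-period days and the food-effect comparison should refer to whichever cohort is recalled. State the basis on which the washout is considered adequate. The choice of interval and visit days belongs to the sponsor, and none is proposed here.

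The cost is schedule wording in the protocol and its copy in the SAP, and possibly a few days' delay to Cohort 4.
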